#### **MRI**

All brain scans will be reviewed and interpreted by one or more neuroradiologists at an independent, central facility with no access (ie, blinded) to treatment assignment thereby avoiding bias.

An MRI manual explaining the instructions for standard image acquisition requirements, data transfer, archiving and shipping, and outlining the phantom data approval process will be provided to all centers.

MRI should not be conducted within 2 weeks of steroid administration due to potential interference.

In case of at least 5 new/enlarged T2 lesions at the MRI of Week 24, an additional MRI will be performed at Week 36.

Then, in case of:

- At least 9 new/enlarged T2 lesions at Week 36, or,
- At least 5 new/enlarged T2 lesions on each of the 2 consecutive MRI scans of Week 36 and Week 48, or,
- At least 5 new/enlarged T2 lesions on each of the 2 consecutive MRI scans of Week 48 and Week 72.

Patients will have the option to continue in an open label teriflunomide treatment arm.

(Note: new/enlarged refer to previous scan)

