#### **11.4.4.2 Analyses of secondary efficacy endpoints**

The proportion of patients relapse-free at Weeks 24, 48, 72 and 96 will be estimated based on Kaplan-Meier methods. Interval estimates will be calculated using 95% point wise confidence intervals.

The number of new or enlarged T2-lesions per MRI scan will be analyzed using a negative binomial regression model. The model will include the total number of new or enlarged T2-lesions as the response variable, with treatment group, region, pubertal status and age as covariates. In order to account for different numbers of MRI scans performed among patients, the log-transformed number of scans will be included in the model as an offset variable. The estimated number of lesions per scan and associated 2-sided 95% CI will be provided for each treatment group. The relative risk, 2-sided 95% confidence interval (CI) and p-value will be provided for comparing teriflunomide to placebo.

The number of T1 Gd-enhancing lesions per MRI scan and the number of new T1 hypointense lesions per MRI scan will be analyzed using a similar negative binomial regression model as described above for T2 lesions.

To reduce the impact of potential outliers, an ordinal logistic regression model including treatment group, region, pubertal status and age will also be used to analyze these endpoints. The following categories for the number of lesions, 0, 1, 2, 3-4 and  $\geq 5$ , are considered and will be further defined in the SAP.

A Poisson regression model with a robust error variance will be used in sensitivity analyses.

Change from baseline in volume of T2 lesions, T1 hypointense lesions and brain atrophy will be analyzed using a mixed-effect model with repeated measures (MMRM) approach with appropriate transformation if necessary. The proportion of patients free of new or enlarged T2-lesions at Weeks 48 and 96 will be summarized based on all patients having an MRI at these time points. More details will be provided in the SAP.

The change from baseline in cognitive outcomes at each visit will be analyzed descriptively.

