2.1.3.2 Secondary efficacy endpoint(s)

The secondary efficacy endpoints pertaining to the open-label period are the following:

- Time to first clinical relapse since enrollment into the open-label period up to the exit of the open-label treatment period
- Proportion of clinical relapse free patients at 24, 48, 72, 96, 120, 144, 168 and 192 weeks
- MRI endpoints at 48, 96, 144 and 192 weeks:
 - Number of new/newly enlarged T2 lesions
 - Number of Gd-enhancing T1 lesions
 - Change in volume of T2 lesions
 - Change in volume of T1 hypointense lesions
 - Number of new hypointense T1 lesions
 - Proportion of patients free of new or enlarged MRI T2 lesions
 - Percentage change of brain volume

The number of new/newly enlarged T2 lesions and the number of Gd-enhancing T1 lesions will be considered the key secondary imaging endpoints.

- Cognitive outcome measured by the SDMT and Cognitive Battery Tests
- Teriflunomide PK
- Exploratory endpoint: proportion of disease-free patients.

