2.4.4 Analyses of efficacy endpoints

All the following efficacy analysis will be conducted on efficacy population, according to the treatment group allocated by randomization in the double-blind period (ie, placebo/teriflunomide versus teriflunomide/teriflunomide). Baseline values of the double-blind period will be used as the baseline in the efficacy analysis for the open-label CSR, unless otherwise noted.

Analyses of efficacy endpoints of the open-period period are of exploratory intent in principle. Long-term treatment effects and the 95% confidence intervals, where applicable, will be assessed since the randomization date in the double-blind period throughout the last visit of the open-label period of the study; unless otherwise noted. P-values will be provided if applicable. No confirmative conclusion should be drawn based on p-value because of exploratory nature of open-label period analysis.

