2.4.4.2.3 Magnetic resonance imaging (MRI) variables

General rules for MRI variables

The protocol requires that the MRI should not be performed until after a minimum of 14 days following completion of corticosteroid therapy. Thus, MRI values obtained within 14 days of systemic corticosteroid therapy will be excluded from the analysis.

Baseline for MRI variables is defined as the last non-missing, valid MRI value that was measured before or on the day of first administration of IMP in the double-blind period. A previous MRI performed in the 6 weeks preceding randomization could be used as the baseline if performed according to the specifications for this study. For valid MRI values in subsequent post baseline visits, time windows (see [Table 4](#) and [Table 5](#) in [Section 2.5.3](#)) between visits will be used to capture MRI measurements. For multiple records within a visit window, the one closest to the targeted visit date will be used.

Number of lesions

The number of new or enlarged T2 lesions per MRI scan will be analyzed using a negative binomial regression model with robust variance estimation. The model will include the total number of new or enlarged T2 lesions as the response variable, with treatment group, region, pubertal status and age as covariates. In order to account for different numbers of MRI scans performed among patients, the log-transformed number of scans will be included in the model as an offset variable. The robust error variances can be estimated by specifying the patient identifier in the repeated statement using SAS PROC GENMOD. The estimated number of lesions per scan and associated 2-sided 95% confidence interval (CI) will be provided for each treatment group.

The number of T1 Gd-enhancing lesions per MRI scan and the number of new T1 hypointense lesions per MRI scan will be analyzed using a similar negative binomial regression model as described above for T2 lesions.

Volume of lesions and brain

Descriptive statistics of the change from baseline in volume of T2 lesions, T1 hypointense lesions and the percentage change of brain volume in the original scale will be summarized at each visit by treatment group.

The proportion of patients free of new or enlarged T2 lesions

The proportion of patients free of new or enlarged T2 lesions at Weeks 48, 96, 144 and 192 will be summarized based on all patients having an MRI at these time points. Kaplan-Meier methods will be used for estimation.

Censoring rule

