2.5.3 Windows for time points

Time window for MRI measurements and SDMT will be used to capture data collected between visits. It is defined in [Table 4](#) and [Table 5](#). Baseline values will be the baseline defined in the double-blind period of the study. All days in the visit window tables for double-blind period ([Table 4](#) and [Table 6](#)) and the open-label period ([Table 5](#) and [Table 7](#)) are relative to the first dose date in each period respectively.

Table 4 - Visit window for MRI variables and SDMT in the double-blind period

Week	Visit	Target day	Schedule A^a	Schedule B^b
0	Baseline	1	Up to 1st dose date	Up to 1st dose date
24	Visit 8	169	after 1 st dose date - 252	after 1 st dose date -210
36	Visit 10	253	Not applicable	211 - 294
48	Visit 12	337	253 - 420	295 - 420
72	Visit 16	505	421 - 588	421 - 588
96	Visit 20	673	589 - Last double-blind dose date + 60 days and before 1st open label dose	589 - Last double-blind dose date + 60 days and before 1st open label dose

^a SDMT and MRI variables for patients without MRI assessment for Week 36

^b MRI variables for patients with MRI assessment for Week 36

Table 5 - Visit window for MRI variables and SDMT in the open-label period

Week	Visit	Target day	SDMT	MRI variables
0	OL transition visit	1	Up to the first dose in OL period	Up to the first dose in OL period
24	OL Visit 7	169	after 1st open-label dose date - 252	Not applicable
48	OL Visit 11	337	252 - 420	after 1st open-label dose date – 504
72	OL Visit 15	505	421 – 588	Not applicable
96	OL Visit 19	673	589 – 756	505 – 840
120	OL Visit 23	841	757 – 924	Not applicable
144	OL Visit 27	1009	925 – 1092	841 – 1176
168	OL Visit 31	1177	1093 – 1260	Not applicable
192	OL Visit 35	1345	1261 - Later of the Last open-label visit date or the 1st dose date in optional additional extension period	1177 - Later of the Last open-label visit date or before 1st dose date in optional additional extension period

For multiple records within a visit window, the one closest to the targeted visit date will be used.

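### With number of scans as exposure, the new/enlarged T2 model understates the lesion rate of the most active patients, because only they get the Week 36 scan

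*Protocol*

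**What the plan says.** Protocol 11.4.4.2 fits a negative binomial model with the "total number of new or enlarged T2-lesions as the response variable", and "the log-transformed number of scans will be included in the model as an offset variable". It reports lesions per scan by arm, and a relative risk with confidence interval and p-value. Protocol 8.1.2 names this count as one of two key secondary imaging endpoints.

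The planned post-baseline scans are at Weeks 24, 48, 72 and 96. Protocol 8.1 (MRI) adds a conditional one: "In case of at least 5 new/enlarged T2 lesions at the MRI of Week 24, an additional MRI will be performed at Week 36". The same section gives the reference for counting: "Note: new/enlarged refer to previous scan". High counts at Week 36, at Weeks 36 and 48, or at Weeks 48 and 72 allow the patient to leave the double-blind period.

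SAP Table 4 has a separate schedule for "MRI variables for patients with MRI assessment for Week 36", in which Week 36 has its own window (days 211-294).

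SAP 2.4.4.2.3 repeats the scan-count offset for the open-label report, "with treatment group, region, pubertal status and age as covariates". On when counting starts, SAP 2.4.4 says that long-term effects "will be assessed since the randomization date in the double-blind period throughout the last visit of the open-label period of the study", unless otherwise noted. SAP 2.1.3.2 lists "MRI endpoints at 48, 96, 144 and 192 weeks" among endpoints pertaining to the open-label period.

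**The concern.** New and enlarging T2 lesions accumulate over time. Number of scans is a sound exposure only if every scan covers about the same interval. Here the outcome itself triggers an additional scan, so the patients with the most lesions are the ones whose intervals are cut from 24 weeks to 12. Their denominator goes up by one and their observation time does not.

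If teriflunomide reduces lesions, more placebo patients meet the trigger. The placebo rate is then deflated more than the teriflunomide rate, and the relative risk understates the effect. A per-scan figure is also not on a common scale when a scan covers 12 weeks in some patients and 24 in others.

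The plan uses time where events accrue elsewhere: the annualized relapse rate model in SAP 2.4.4.3.1 has log treatment duration as its offset.

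**Working it through.** The documents give no lesion rate, power or sample size for this endpoint, so there is no stated figure to reproduce.

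**1. One patient with the extra scan.** Assume constant accrual and counts that add across intervals. Per-scan rate divided by true rate per 24 weeks = (weeks observed / 24) / number of scans.

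| Last scan | Scans | Weeks per scan | Ratio | Understated by |
|---|---|---|---|---|
| Week 36 | 2 | 36/2 = 18 | 1.5/2 = 0.75 | 25% |
| Week 48 | 3 | 48/3 = 16 | 2/3 = 0.67 | 33% |
| Week 72 | 4 | 72/4 = 18 | 3/4 = 0.75 | 25% |
| Week 96 | 5 | 96/5 = 19.2 | 4/5 = 0.80 | 20% |

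Example: 8 lesions per 24 weeks gives 32 over 96 weeks. That is 32/4 = 8.0 per scan without the Week 36 scan and 32/5 = 6.4 with it. Patients scanned every 24 weeks have ratio 1.00.

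**2. Lesions counted twice.** A lesion in the split interval may count as new at Week 36 and as enlarged at Week 48. Let d be the share counted twice.
- Exit at Week 48: the relative error is d/2 with time and (1-d)/3 with scans. Setting them equal gives 3d = 2 - 2d, so d = 0.40.
- Week 96: d/4 = (1-d)/5 gives 5d = 4 - 4d, so d = 0.44.

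Time is closer to the truth unless more than about 40-44% of lesions in that interval are counted twice.

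**3. Effect on the rate ratio.** Lesion rates and dispersion are assumptions. The simulation used 2:1 allocation and gamma frailty (dispersion 1 or 2), with 3, 5 or 10 placebo lesions per 24 weeks. Scan and exit rules came from Protocol 8.1, and relapse hazards (0.4581 and 0.2291) and 20% dropout from Protocol 11.1. It was run with and without a scan at discontinuation, with 60,000 patients per scenario (120,000 for no effect).

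| True ratio | Scans as exposure | Time as exposure | Gap |
|---|---|---|---|
| 0.50 | 0.51-0.55 | 0.49-0.52 | 0.01-0.04 |
| 0.70 | 0.71-0.73 | 0.69-0.71 | 0.00-0.03 |
| No effect on lesions or relapse | | | 0.001 or less |

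At true 0.50, 19-54% of placebo and 7-37% of teriflunomide patients had a Week 36 scan. Power at 165 patients changed by at most 5 points. With no lesion effect but the plan's relapse hazards, the gap was -0.01 to 0.00. If relapse risk rises with lesion rate, both exposures drift (time gives 0.51-0.55 at true 0.50). The gap is still 0.00-0.04, so the offset does not cause that drift.

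A simpler simulation (30,000 per arm; placebo 2, 4 or 8 lesions per 24 weeks; no relapse exits or dropout) gave 0.52-0.55 per scan at true 0.50 and 0.72-0.73 at true 0.70. With time it gave 0.49-0.51 and 0.69-0.72. Its largest gap was 0.544 - 0.496 = 0.048, at 4 placebo lesions, dispersion 1 and exit rules on. In that case 33% of placebo and 13% of teriflunomide patients met the trigger. The fitted placebo rate was 3.39 per scan against 4.02 per 24 weeks, and the teriflunomide rate 1.84 against 2.00.

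**4. Open-label report.** If counting starts at randomization, intervals of 12, 24 and 48 weeks each count as one scan. Over the same 192 weeks:
- a double-blind completer with the extra scan has 5 + 2 = 7 scans, or 192/7 = 27.4 weeks each;
- a patient without it who switches at Week 48 has 2 + 3 = 5 scans, or 192/5 = 38.4 weeks each.

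At identical lesion rates their per-scan rates differ by 38.4/27.4 = 1.40, that is 40%.

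**5. Baseline covariate (side point).** The count models omit the baseline MRI value. In 400 simulated trials of 165 patients per setting, adding log(1 + baseline count) cut the standard error by about 1%, 4% and 10% at assumed rank correlations of 0.2, 0.37 and 0.5. The omission costs precision only.

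**The case against.** The strongest objection is that the governing document is missing. SAP section 2 says the double-blind analysis was covered in a separate SAP, and Protocol 11.4.4.2 defers details to it. That SAP could pool or drop the Week 36 scan. This stands and limits confidence. Nothing supplied shows such a correction, though.

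Two premises are partly inferred. The previous-scan note sits beside the switching criteria, not the endpoint definition, and Table 4 does not say that Week 36 enters the offset. But the note is the only reference-scan rule in the documents, and a window of its own is most naturally read as a scan of its own.

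The planned ordinal logistic analysis has a top category of 5 or more. On a total-count reading, a triggered patient is already there, so the extra scan changes nothing. That is fair, but this analysis yields no rate ratio and states no time-based exposure. The robust Poisson sensitivity analysis states none either.

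The protocol names its quantity per scan, so too low presumes a rate over time as the target. That is true, but the per-scan quantity then depends on a schedule driven by the outcome.

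On the open-label side, no conditional scan exists after the switch, and SAP 2.4.4 and 2.4.4.4 call the analyses exploratory. If counting starts at open-label entry, the Week 36 problem is absent there. The bias is also conservative, and the endpoint lies outside multiplicity control (Protocol 11.4.4.3). These points limit the importance and leave the mechanism intact.

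**Conclusion.** The concern holds. As written, the exposure term understates the lesion rate over time of patients with the Week 36 scan by 20-33%, given additive counts and constant accrual. If the drug works, the double-blind rate ratio moves toward 1 by about 0.01-0.04 at a true 0.50 and 0.00-0.03 at a true 0.70, under the assumed lesion rates. The simpler simulation reaches 0.05.

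The distortion works against teriflunomide and creates no false positive when the drug affects neither lesions nor relapse. It should be corrected because it is directional, touches a key secondary endpoint with a planned relative risk and p-value, and is nearly free to remove. Confidence is medium, mainly because the double-blind SAP was not available. The unstated starting point in the open-label SAP needs clarifying in any case.

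**What to change.** - In Protocol 11.4.4.2 and SAP 2.4.4.2.3, for new/enlarged T2 and new T1-hypointense counts, set the offset to log(weeks from the reference scan to the last included scan, summed over the intervals whose counts are included).
- Keep log(number of scans) for Gd-enhancing lesions, which are a snapshot at each scan.
- State in SAP 2.4.4.2.3 whether counting starts at randomization or at open-label entry, and how an interval is treated when its scan is excluded for recent corticosteroids.
- Optionally, add a baseline MRI value (Gd count or T2 volume), with a stated rule for patients without a valid baseline scan.
- If the double-blind data are already unblinded, leave the prespecified model as it is and report the time-based fit beside it as a sensitivity analysis.

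The cost is one offset term and one optional covariate, from scan dates and counts already collected. Results then read as lesions per unit time, and per-scan figures can stay as a descriptive summary.

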### **4.2 SECONDARY OBJECTIVE(S)**

The secondary objectives of this study are as follows:

- To assess the effect of teriflunomide in comparison to placebo on disease activity/progression measured by brain MRI and on cognitive function.
- To evaluate the safety and tolerability of teriflunomide in comparison to placebo.
- To evaluate the pharmacokinetics (PK) of teriflunomide.

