#### **10.1.3.4 Assessments performed on the EOT or premature treatment discontinuation**

Patients who complete the treatment period or who prematurely discontinue should complete EOT procedures including both safety and efficacy assessments. This visit does not need to be performed when the patient switches to the open label period after a confirmed relapse or high MRI activity (as per protocol criteria). Prematurely discontinued patients are encouraged to participate in an early permanent treatment discontinuation (EPTD): they will be followed for safety until they complete 96 weeks from randomization. This includes discontinuation from the open label period, when it occurs within 96 weeks of randomization.

- EDSS.
- SDMT.

- Cognitive Battery Test.
- Brain MRI.
- Adverse event reporting.
- Vital signs.
- Physical examination.
- ECG 12-leads.
- Tanner staging.
- Clinical routine laboratories (including immunoglobulins and TSH).
- Concomitant medication.
- Accountability / compliance.
- Teriflunomide PK sampling.

Post drug elimination process (ie, prescribing Cholestyramine or Activated charcoal and scheduling for two follow up visits) should be initiated.

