### 11.1 DETERMINATION OF SAMPLE SIZE

The sample size calculation is based on the primary efficacy endpoint, time to first confirmed relapse after randomization. Assuming 60% of placebo patients will experience a relapse by 2 years, 165 children aged 10 to <18 years (110 teriflunomide and 55 placebo; including approximately 20% pre-pubertal patients or 10% of patients under the age of 13 years at time of inclusion into the study and at least 25% male patients) are needed for 80% power to detect a hazard ratio (teriflunomide versus placebo) of 0.5 (2-sided alpha 0.05). The 2-year rate of relapse in the teriflunomide group would be 36.8% and the corresponding hazard rates, assuming the time-to-relapse is exponentially distributed with a constant hazard rate, would be 0.4581 for placebo and 0.2291 for teriflunomide. The sample size is adjusted assuming 20% of patients discontinue the study in 2 years due to reasons other than relapse. Calculations are performed using nQuery Advisor 7.

The assumption for the percentage of placebo patients with relapse at 2 years is based on the combined data from the completed Phase III monotherapy adult studies (EFC6049/TEMPO and EFC10531/TOWER), where 58.7% of placebo patients aged  $\leq 30$  (n=167) experienced at least 1 relapse in a 2-year treatment period. Of note, the corresponding percentage was 38.7% in the 163 patients aged  $\leq 30$  treated with teriflunomide 14 mg.

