2.4.4.2.5 Cognitive outcome

The change from baseline in Cognitive Battery Tests and SDMT will be summarized descriptively. Box plot will be provided as well.

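### Cognition has a secondary objective of comparison with placebo but only a descriptive analysis, and its late-visit means would compare unequally depleted arms

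*Protocol*

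**What the plan says.** Protocol section 4.2 gives as a secondary objective: "To assess the effect of teriflunomide in comparison to placebo on disease activity/progression measured by brain MRI and on cognitive function". The Clinical Trial Summary repeats it. Imaging and cognition thus share one comparative sentence.

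Protocol section 11.4.4.2 treats the two halves differently. For imaging, lesion counts get negative binomial models with a relative risk, 95% CI and p-value, and for the volumes: "Change from baseline in volume of T2 lesions, T1 hypointense lesions and brain atrophy will be analyzed using a mixed-effect model with repeated measures". For cognition the whole plan is: "The change from baseline in cognitive outcomes at each visit will be analyzed descriptively". The Clinical Trial Summary also says descriptive.

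The Clinical Trial Summary schedules SDMT at randomization, every 24 weeks and at end of treatment (EOT), and the cognitive battery at randomization and EOT only. Section 5.1 gives patients the option of open-label treatment after a relapse that follows the 8-week run-in and is confirmed by the adjudication panel, or on high MRI activity. Section 10.1.3.4 puts SDMT and the battery in the EOT visit, then says: "This visit does not need to be performed when the patient switches to the open label period after a confirmed relapse", and extends this to high MRI activity.

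The supplied SAP covers the open-label period. Its section 2.4.4.2.5 reads: "The change from baseline in Cognitive Battery Tests and SDMT will be summarized descriptively". Its section 2 says that a separate SAP, not among the documents, covers the double-blind analysis.

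**The concern.** An objective worded as a comparison with placebo needs a comparison: a difference between arms with an interval. As the documents stand, the reader gets by-arm summaries and must subtract them.

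That subtraction becomes less safe with time. A confirmed relapse opens the way out of the blinded phase, and relapse is expected more often on placebo. No cognitive test is required at the switch: the EOT visit is waived, the relapse-visit list in section 10.1.3.5 contains no SDMT, and the open-label flow chart in section 1.3 shows its first SDMT at open-label Week 24. The follow-up items named in section 10.3.2 for patients who stop treatment include no cognitive test. The Week 96 double-blind SDMT window in SAP section 2.5.3 (Table 4) closes before the first open-label dose. Later means therefore describe groups filtered by the primary outcome, more heavily on placebo.

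At stake is whether the trial can say anything sound about cognition against placebo, and whether an unadjusted Week 96 contrast is read as a drug effect.

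**Working it through.** **Inputs (Protocol section 11.1).** "Assuming 60% of placebo patients will experience a relapse by 2 years"; "The 2-year rate of relapse in the teriflunomide group would be 36.8"%; hazards of 0.4581 and 0.2291 per year; 20% discontinuing in 2 years for reasons other than relapse; 55 placebo and 110 teriflunomide patients.

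**Reproducing the plan's own figures.**
- Relapse by 2 years: 1 − exp(−2 × 0.4581) = 60.0% and 1 − exp(−2 × 0.2291) = 36.8%. Both match.
- Dropout hazard: δ = −ln(0.8)/2 = 0.1116 per year.
- Event probability with dropout: λ/(λ+δ) × [1 − exp(−2(λ+δ))] = 0.547 on placebo and 0.332 on teriflunomide.
- Log-hazard sample size at 2:1: (1.960 + 0.842)² × (3/0.547 + 1.5/0.332)/(ln 2)² ≈ 163, with 80.4% power at 165. A hazard-difference version gives 168. The stated 165 for 80% power is reproduced within the spread of standard formulas, so these inputs are a fair basis for projection.

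**Patients still in the blinded phase.** n(t) = N × exp(−(λ+δ)t), with t in years (weeks × 7/365.25). At Week 96, t = 1.84:
- Placebo: 55 × exp(−0.5697 × 1.84) = 19.3.
- Teriflunomide: 110 × exp(−0.3407 × 1.84) = 58.8.

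The last column below is the approximate 95% half-width of a single-visit difference, 1.96 × √(1/nP + 1/nT), in SD units because the documents give no SDMT standard deviation.

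| Week | Placebo | Teriflunomide | Half-width (SD) |
|---|---|---|---|
| 24 | 42.3 (77%) | 94.0 (85%) | 0.36 |
| 48 | 32.6 (59%) | 80.4 (73%) | 0.41 |
| 72 | 25.1 (46%) | 68.7 (62%) | 0.46 |
| 96 | 19.3 (35%) | 58.8 (53%) | 0.51 |

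With all 55 and 110 measured, the half-width would be 0.32. Week 96 retention is 78 of 165 (47%) overall and differs by about 18 percentage points between arms.

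**Sensitivity at Week 96.**
- No dropout: 23.7 and 72.2.
- Relapsers in the first 8 weeks stay in: 20.7 and 60.9.
- Extra loss to high MRI activity, for which the documents give no rate. Assuming 10% to 30% on placebo and 5% to 15% on teriflunomide: about 14 to 17 and 50 to 56.

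The imbalance persists in every case.

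**Illustration of selection bias (assumed values).** Suppose treatment has no effect on cognition, relapse-proneness correlates 0.2 to 0.6 with worse cognitive change, log-frailty SD is 0.5 to 1.0, and 2-year relapse rates are 60% and 36.8%. Simulated completer means then differ by −0.04 to −0.17 SD, against teriflunomide, because the placebo completers are the more strongly selected. The documents supply none of the correlation or frailty values, so this shows a plausible direction and order of size only.

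**The case against.** Several points on the other side stand.

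- **The double-blind SAP is unseen.** A reader might infer that the plan as a whole has no cognitive effect estimate. The documents do not support that; the absence is shown only for the protocol and the open-label SAP.
- **Week 96 is not confined to a few relapse-free patients.** A reader might infer that it is. Some 53% of the teriflunomide arm is expected to remain. Relapses in the run-in, or not confirmed by the panel, do not open the switch, and switching is optional. Patients also leave for high MRI activity or other reasons. Early discontinuers are asked for an EOT test, though section 11.4.4.2 does not say how it is used. The counts above are approximations.
- **Maturation and practice do not bias the placebo comparison.** A reader might infer that raw change mixes them with drug effect. In concurrent randomized arms tested on the same schedule they are expected to act alike, apart from differential attrition. They matter for within-group change in the open-label data, which the protocol calls non-controlled and supportive.
- **A model is not a cure.** A mixed model relies on missing-at-random, and patients who switch before Week 24 may have no post-baseline blinded SDMT. A baseline-adjusted battery comparison at EOT keeps the same selected patients.
- **Cognition is not a key secondary endpoint** and carries no multiplicity-controlled claim. A descriptive secondary analysis is permissible in itself.

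The last point does not close the gap. The MRI volumes also carry no multiplicity-controlled claim, yet section 11.4.4.2 models them. Rewording the objective as descriptive would remove the mismatch on paper but give up a comparison that randomization and the existing SDMT schedule allow.

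**Conclusion.** The point holds within limits, and the change should be made. In the protocol and the supplied SAP, a comparative objective on cognition has no between-arm estimate or interval, and the protocol already names a suitable method for repeated continuous outcomes. By-visit means rest mainly, not solely, on patients still in the blinded phase, with about 35% of placebo and 53% of teriflunomide patients projected at Week 96. That projection assumes exponential relapse and dropout at the protocol's rates and exit at every relapse; the sensitivity cases shift the counts but keep the imbalance. The size of any resulting bias cannot be fixed from the documents. The conclusion is conditional on the double-blind SAP, which may already contain such an analysis.

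**What to change.** For the double-blind period, add a mixed model for repeated measures of SDMT change with treatment, visit, treatment-by-visit, baseline SDMT, age, region and pubertal status. Report the adjusted difference with 95% CI at Week 96 and averaged over visits, with the number contributing per arm and visit. State the estimand for patients who switch, how early discontinuers' EOT tests enter, and that the model assumes missing-at-random. Label the analysis exploratory, and post hoc if the double-blind report is closed.

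The cognitive battery has one post-baseline time point. Report a baseline-adjusted difference with 95% CI among those tested at EOT, give the number of switchers untested, and say plainly that this does not remove selection.

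The cost is a few model runs on data already collected. The downside is an additional exploratory, imprecise estimate that must be labelled as such: the single-visit half-width at Week 96 is about 0.5 SD, and borrowing earlier visits should narrow it somewhat.
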